involve multiple components, at least one of which is always applicable; some components are only applicable to a subset of clients, eg HCP counsels the woman about mental health is only applicable if the client's response to a previous question is cause for concern. All essential components will carry a weight of 1. The overall score will be derived by aggregating the weighted scores for each essential component which will then be converted to a percentage. Six essential components are binary; hence the score can only be 0 (not achieved), or 1 (achieved and single weighted); in some cases the determination of this involves an algorithm. The other seven essential components are not binary as they have sub-components assessed independently and thus may be partially achieved and carry an intermediate score, eg a multiple of 0.25 for essential component 1 (respectful maternal care).

Outcome 2: Essential components included in the composite measure of integrated services specific to PNC visits are listed below.

- EC1b = Respectful maternity care indicators:
 - Introductions, greeting the woman, consent, questions
- EC2b = Screening for Pre-eclampsia:
 - Measure BP
- EC3b = Screening for, prevention and management of Anaemia:
 - Measure Haemoglobin
 - Provide ferrous sulphate with folic acid
- EC4b = Screening for, prevention and management of Malaria:
 - Checked for clinical symptoms and test for Malaria if relevant
 - Provide bed nets if not provided yet
- EC5b = Screening for, prevention and management of HIV:
 - Test for HIV
 - Provide Prevention of mother to child transmission care (PMTCT)
 - Provide anti-retroviral drugs (ARV) for mother and baby
- EC6b = Screening for, prevention and management of Syphilis:
 - Test for syphilis
 - Provide antibiotics if needed
- EC7b = Screening for, prevention and management of Tuberculosis (TB):
 - Checked for clinical symptoms and test for TB
 - First line TB drugs or referral if needed
- EC8b = Prevention of Tetanus in mother and baby:
 - Tetanus toxoid vaccination
- EC9b = Screening and counselling for mental health and domestic violence:
 - Screening tools
 - Counselling services
- EC10b = Provide advice and support regarding breastfeeding:
 - Consultation

- EC11b = Offer postpartum contraception:
 - Consultation
- EC12b = Monitor newborn growth:
 - Weigh the baby
- EC13b = Clinical examination of the mother:
 - Examine the mother
- EC14b = Clinical examination of the baby:
 - Examine the baby

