- EC15b = Immunization status checked and required vaccinations offered and provided if required
- EC16b = Provide advice on danger signs in the mother and baby:
 - Consultation

The outcome for each PNC visit will be a score which measures the proportion of the above components that was delivered during that visit (EC_PNC). This score will be derived in a similar manner to the score for ANC, the difference being that three essential components used for ANC will be dropped and six others added.

The observation tool is detailed in **Appendix 2**.

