Appendix 2: Tools for data collection for observation

Below is the observation checklist. Essential components are numbered slightly differently than appendix 1 for the construction of the score. The scoring attributes will not appear for the data collectors and only be used by the statistician at time of analysis. Each essential component is score 1, for a total of 13 essential components for ANC visits, and 16 for PNC visits. Essential components can be a sum of x number of subcomponents as indicated in the table. Each subcomponent needs all applicable questions to be observed (Please see examples of algorithms at the end of appendix).

Please note this tool is to be deployed on an electronic platform, therefore the formatting of the tool will be visually different to what is included here. All boxes starting with "If" will only appear depending on the answer to the relevant condition (e.g. treatment will only be asked for women tested positive). The "Not applicable" answer is available for questions which depend on the gestational age and type of visit. The tool will be deployed in FRENCH.

OBSERVATION

Variable label	Answers	Conditionality	Scoring
GENERAL			
Please select the region	[dropdown menu]		
Please select the name of the facility	[dropdown menu]		
If 'Other' facility, please specify	[free text]		
Date of survey	[select from calendar]		
Name of person completing form	[free text]		
Anonymous ID of HCP	[free text]		
ANC			
ANC general information			
First/subsequent contact	0 - Subsequent contact, 1 - first contact -99 INF		
Which subsequent visit was it?	2- ANC2, 3- ANC3, 4- ANC4, 5- ANC5, 6-ANC6, 7- ANC7, 7-ANC8	Only to appear if previous answer = 0 – Subsequent visit	
Gestational age (weeks)	[integer]		
Who gave information about gestational age	1 - Woman, 2 - Healthcare provider, 3 - Other (specify)		
If other, specify	[free text]		
Women arrival time in the facility	[time]		
Comments	[free text]		

ANC contact		
EC1: Respectful maternity		1 (sum of all
care		subcomponents)
RMC subcomponent 1		0.25 (Points given if all applicable questions are observed)
The healthcare provider		
(HCP) introduced		
themselves to the		
pregnant woman	0 - No, 1 - Yes	
The HCP greeted the		
pregnant woman (or		
answered if woman		
greeted first)	0 - No, 1 – Yes	
RMC subcomponent 2		 0.25
The HCP asked the		
pregnant woman to take a	0 - No, 1 - Yes, -88 - Not	
seat	applicable (no chairs)	
The HCP asked the		
pregnant woman if she		
came with a companion		

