HCP checked the perineum	0 - No, 1 - Yes	
to look for scar of any	,	
perineal tear and/or		
episiotomy performed		
HCP checked the abdomen	0 - No, 1 - Yes	
to see if any wound from	,	
caesarean section		
HCP recognised and acted	0 - No, 1 - Yes, -88 - Not	
upon abnormal findings	applicable (no abnormal	
with abdominal or	findings)	
perineum examination		
Mother exam		0.5
Subcomponent 3		
HCP asked about urination	0 - No, 1 - Yes	
and urinary continence		
HCP asked about bowel	0 - No, 1 - Yes	
function		
HCP asked the woman	0 - No, 1 - Yes	
about signs of Deep vein	0 110, 1 100	
thrombosis in her legs		
HCP gave the woman	0 - No, 1 - Yes	
hygiene advice	,	
HCP recognised and acted	0 - No, 1 - Yes, -88 - Not	
upon abnormal findings	applicable	
EC14b = Clinical		1
examination of the baby		
HCP observed hygiene	0 - No, 1 - Yes	
measures before		
examining the baby		

Have the newborn's eyes	0 - No, 1 - Yes	1	 
been checked?	0 - 100, 1 - 163		
Was the temperature of	0 - No, 1 - Yes		
the newborn taken with a	0 - 100, 1 - 163		
thermometer?			
Has the HCP listened to	0 - No, 1 - Yes		
the heartbeat of the	0 - 100, 1 - 163		
newborn (auscultation)?			
Did the HCP examine the	0 - No, 1 - Yes		
abdomen of the newborn	0 - 100, 1 - 163		
(palpation)?			
Has the HCP checked the	0 - No, 1 - Yes		
umbilical cord of the	0 140, 1 163		
newborn?			
Has the HCP checked if the	0 - No, 1 - Yes		
newborn is passing urine	1, 2		
Has the HCP checked if	0 - No, 1 - Yes		
the newborn has passed	1, 2		
stools or opened its			
bowel?			
Has the newborn been	0 - No, 1 - Yes		
weighed?			
HCP completed the baby's			
growth chart			
	0 - No, 1 - Yes, -88 - Not		
HCP recognised and acted	applicable (no abnormal		
upon abnormal findings	findings)		
EC15b = Immunization			1
status checked and			
required vaccinations			
offered and provided			
HCP checked whether	0 - No, 1 - Yes		
newborn vaccines are up-			
to-date			
HCP offered appropriate	0 - No, 1 – Yes, -88 Not		
vaccination	applicable		
EC16b = Provide advice on			1
danger signs in the			
mother and baby			
HCP gave advice on	0 - No, 1 - Yes		
danger signs (i.e. signs that			
indicate the baby is sick) to			
look out for in the baby			
HCP gave the date of the	0 - No, 1 - Yes	Does not	
next PNC contact to the		appear if PNC	
mother		visit = W6	
Woman departure/exit	[enter time]		
time			
Comments	[free text]		

SCORING EXAMPLE: Respectful Maternity Care essential component

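### Weighing the baby is its own PNC component in section 3.4 but is also a required row of the baby examination in the Appendix 2 tool, so omitting it can cost up to 2 of 16 points

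*Protocol*

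**What the plan says.** Protocol section 3.4 lists sixteen components for the PNC score, one of the trial's two primary outcomes. Two concern us: "EC12b = Monitor newborn growth", whose single item is weighing, and "EC14b = Clinical examination of the baby". On weights it says "All essential components will carry a weight of 1". Partial credit is reserved for components that are "not binary as they have sub-components assessed independently and thus may be partially achieved"; this is written for ANC, and the PNC score is to be derived in a similar manner.

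Appendix 2 repeats the count: "Each essential component is score 1, for a total of 13 essential components for ANC visits, and 16 for PNC visits". Its rule for credit is "Each subcomponent needs all applicable questions to be observed". Its EC14b block carries one weight of 1 and no subcomponents. Among its rows are one that begins "Has the newborn been" and asks about weighing, answered yes or no with no not-applicable option, and one on completing the baby's growth chart.

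Two other appendices place weighing with growth. Appendix 1 gives newborn growth (item 18) the baby scale and the weight chart, and gives clinical examination (item 19) only an examination area and couch. In Appendix 3, a missing baby scale is a reason for growth monitoring being unavailable (da058) but is not among the named reasons for examination being unavailable (da060).

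**The concern.** The same act appears in two places with different roles. In section 3.4 it is the whole of the growth component. In the tool it is one condition for the examination component. If both apply, a provider who performs every examination step but does not weigh the baby loses the growth point, as intended, and also the entire examination point.

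Two uses of the data are exposed. First, the PNC primary outcome gives weighing more influence than its own component implies, and that extra influence grows as the rest of the examination becomes more complete, which is the state the training aims for. Second, sections 3.2.3 and 3.7 plan to relate component delivery to availability of equipment. A missing baby scale would be logged under growth in Appendix 3 while the zero appears under examination, where Appendix 3 may record the service as available. That part of the shortfall would then look like provider practice.

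**Working it through.** **1. Component count.** Section 3.4 says of the PNC score, relative to ANC, "the difference being that three essential components used for ANC will be dropped and six others added": 13 − 3 + 6 = 16. The section 3.4 list runs from EC1b to EC16b, also 16, and Appendix 2 states 16. The three agree. One component is worth 1/16 = 6.25 percentage points.

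**2. Does the tool still have a growth component?** The readable part of Appendix 2 shows EC1b to EC9b (9 components) and EC13b to EC16b (4), so 13. Then 16 − 13 = 3 remain, and the section 3.4 components not otherwise seen under a heading are breastfeeding, contraception and newborn growth. By elimination growth keeps its own point, though the rows scored under it cannot be read.

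**3. How EC14b is scored.** It has one weight, no subcomponents, and falls under a rule requiring all applicable questions. EC13b, directly above it, is split 0.25/0.25/0.5, so the absence of a split at EC14b looks deliberate. All-or-nothing is the fair reading, although it is not written at EC14b itself.

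**4. Rows in EC14b.** Unconditional: hygiene, eyes, temperature, auscultation, abdomen, cord, urine, stools, weighing, growth chart = 10, so 9 besides weighing. Conditional: action on abnormal findings = 1.

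**5. Loss from not weighing.**

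Loss = 1/16 (EC12b) + (1/16) × P(all other applicable EC14b rows done)

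- Ceiling, when everything else is done: 2/16 = 12.5 points, of which 6.25 is intended and 6.25 is excess.
- Floor, when any other row is missed: 1/16 = 6.25 points, with no excess.

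**6. Average excess between these limits.** Assume that the nine other unconditional rows are independent with common probability p, and that the conditional row does not apply. Then excess = 6.25 × p⁹.

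| p | p⁹ | Excess (points) | Total loss (points) |
|---|---|---|---|
| 0.5 | 0.0020 | 0.01 | 6.26 |
| 0.8 | 0.1342 | 0.84 | 7.09 |
| 0.9 | 0.3874 | 2.42 | 8.67 |
| 1.0 | 1 | 6.25 | 12.50 |

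The value 0.5 matches the baseline delivery assumed in section 3.8; the other values are illustrative.

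**7. Effect on a before-after contrast.** Suppose, purely for illustration, that weighing rises from 60% to 90% with the other rows held at p. EC12b contributes 0.30 × 6.25 = 1.88 points. EC14b adds 0.30 × 6.25 × p⁹: about 0.004 at p = 0.5, 0.25 at 0.8, 0.73 at 0.9, and 1.88 at most. The detectable difference in section 3.6 is 0.23, or 23 points.

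**The case against.** The strongest reply is that the tool's growth rows are not readable, so nobody can show from this text that the tool scores weighing twice. The tool does not copy section 3.4 exactly either: it swaps EC2 and EC3, and family-planning rows stand directly before EC13b, where section 3.4 has newborn growth. This stands as a limit on what can be claimed. It does not remove the conflict. If the growth component scores weighing, weighing counts in two components; if it does not, the tool departs from section 3.4, where weighing is the component's only item.

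A second reply is that section 3.4 allows an algorithm for some binary components, and Appendix 2 refers to worked algorithms at its end that are not visible beyond one heading. All-or-nothing scoring of EC14b is therefore a reading, though the natural one.

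A reader might infer that weighing always carries two of the 16 points. The documents do not support that. Weighing settles EC12b by itself, but it is only one of ten unconditional rows in EC14b and decides that point only when all the others are met. Nor does a day without a scale move every visit by 12.5 points: half of that is the intended EC12b loss, and the other half needs a complete examination at every visit. Appendix 5 also puts baby scales on the supply list, Appendix 3 records their absence, and the protocol says shortages will be observed as such and analysed by intention to treat.

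A reader might also infer that equal weighting of components is broken. It is not: every component still has a weight of 1. What becomes unequal is the influence of a single act across components.

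**Conclusion.** The protocol is inconsistent about where weighing the baby is scored in a primary outcome. Section 3.4 and Appendices 1 and 3 place it with growth monitoring; the Appendix 2 tool also makes it, together with the growth chart, a condition for the examination point.

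The consequence is bounded and usually modest. Omitting weighing costs between 6.25 and 12.5 points, and only the part above 6.25 is unintended. That part is negligible at 50% row delivery and reaches about 2.4 points at 90%, under independence and equal probabilities. Positive correlation between rows would raise these averages, but never above 6.25. The effect on the estimated training benefit is smaller still, because it is multiplied by the change in the weighing rate.

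The conclusion rests on two inferences: that EC14b is all-or-nothing, and that the tool retains a growth component that scores weighing as section 3.4 defines it. Whichever way the second turns out, the passages need to be reconciled.

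**What to change.** Reconcile section 3.4 with Appendix 2. Score the weighing and growth-chart rows once, under the newborn-growth component, and derive EC14b from the examination rows only: hygiene, eyes, temperature, auscultation, abdomen, cord, urine, stools, and action on abnormal findings. State at EC14b whether it is all-or-nothing. Before editing, check the tool's growth rows in the full form so that nothing is scored twice or lost.

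Appendix 2 says that scoring attributes are hidden from data collectors and applied by the statistician at analysis. The rows can therefore stay where they are in the form. The cost is one line in the scoring specification and a small change to the script, with no new data, and it should be settled before outcome data are examined.

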Appendix 5: Healthcare Facility Improvement Fund (HFIF) – List of equipment and consumables

The following list of equipment and consumables is defined by the CMNH-LSTM experts as essentials to be provided within the HFIF at the beginning of the trial. The definitive list and amount attributed to each facility will be finalized in accordance with the MSP based on the latest update of the data retrieved during the previous HFA.

Essential equipment list for ANC

- Sphygmomanometer with standard and large cuff
- Stethoscope
- Thermometer
- Tape measure (plastic and flexible)
- Pinard stethoscope
- Examination couch
- Curtain
- Adult weighing scales
- Sheets/material for privacy
- Fetal doppler and batteries

Essential equipment list for PNC

- Sphygmomanometer with standard and large cuff
- Stethoscope
- Thermometer
- Tape measure (plastic and flexible)
- Examination couch
- Curtain
- Sheets/material for privacy
- Baby weighing scales
- Thermometer

Essential consumables for ANC and PNC

- Urine dipsticks (detect protein as a minimum)
- Alcohol rub for hands
- Pre injection alcohol swabs
- Non-sterile + sterile gloves
- Microbiology swabs
- Cotton wool/small gauze swabs
- Needles 21 gauge for IM injection
- 1, and 5 ml syringes
- Blood bottles and needles for venous samples
- Needles- neonate 23 or 25 gauge for IM injection
- Sterile scissors and staple removers
